3.2 STUDY ENDPOINT RATIONALE

Study endpoints are stratified by disease severity (tdMeta or μ Meta). Study endpoints include traditionally accepted trial endpoints in single-arm oncology studies including objective response rate (ORR), duration of response (DoR), disease-free survival (DFS), and overall survival (OS)¹¹. The study also leverages real-world endpoints of time to next treatment (TTnT) and time to treatment discontinuation (TTD), and another potential surrogate endpoint of ctDNA response rate as defined in **Table A** and further described below.

3.2.1 REAL-WORLD ENDPOINTS

Increasingly, real-world evidence is being looked to as a complement to traditional clinical trial data collection. Real-world data is often easier and less expensive to collect, especially if it can be exported directly from electronic health record systems. The 21st Century Cures Act mandates the creation of regulatory pathways to support real-world evidence based regulatory approvals for the expanded use of existing FDA-approved therapies. For this study, we sought

The information contained in this protocol and all other information relevant to this study are confidential and proprietary information of Strata Oncology Inc., except as may be required by federal, state or local laws or regulation, and may not be disclosed to others without prior written permission of Strata.

Page 21 of 56

to leverage both traditional and real-world data collection methodologies to reduce future data collection burden.

OS is well established as a standard measure of clinical benefit in cancer drug development. Additionally, surrogates are often used to support drug and/or medical device development as they have reduced event timelines. The changes “induced by a therapy on a surrogate endpoint are expected to reflect changes in a clinically meaningful endpoint”.¹²

TTnT and TTD will additionally be used as potential surrogates to OS. Khozin and colleagues looked at programmed death-ligand 1 (PD-L1) therapy outcomes for NSCLC participants within the Flatiron dataset and found that overall survival was strongly correlated with real world TTD ($r^2=0.81$, 95% CI 0.80-0.82) and also modestly correlated with TTnT ($p = 0.60$, 95% CI 0.56-0.64).¹³ Similar results were observed across six different datasets (N=269-6,924) for NSCLC participants treated with immunotherapies. Correlations between the real-world endpoints of real-world TTD and real-world TTnT and OS were moderate to high and the authors concluded “real-world end points are generally consistent with each other and with outcomes observed in randomized clinical trials, which substantiates the potential validity of real-world data to support regulatory and payor decision making”.¹⁴

As high and significant correlation does not necessarily capture off-target effects and does not equal causation, Prentice has posited that it may be sufficient if the surrogate captures the net effect of the intervention on the clinical efficacy measure.¹⁵ OS inherently captures not only the study drug's efficacy, but also any downstream therapies the participant might have been administered.¹³ Real-world TTnT and real-world TTD may provide more clinically meaningful endpoints as they also take into account why physicians and participants alter clinical care including toxicity and efficacy of the current drug under study. These surrogates are censored less commonly compared to OS.¹⁴ While we may not have a comprehensive understanding of all factors, the most reliable evidence regarding the validity of a surrogate endpoint for a clinical efficacy measure might be provided by numerous trials which give reliable estimates of the net effects of the intervention on the clinically meaningful endpoint such as overall survival and the surrogate.¹⁶ As in previous studies, this study will assess both the proposed surrogates (real-world TTnT and real-world TTD) and the known clinically meaningful endpoint of OS for the primary objectives.

3.2.2 CTDNA RESPONSE RATE

ctDNA clearance or response has been shown to be an early predictor of therapy response.^{17,18} The current study will leverage ctDNA response rate as the secondary endpoint in both tdMeta and μ Meta cohorts. ctDNA response rate is defined as the proportion of participants with a <50% ratio of mean VAF. An individual's molecular response is calculated as a ratio of mean VAF on-treatment at 6 months to their baseline VAF. This is based on the tracer markers based

The information contained in this protocol and all other information relevant to this study are confidential and proprietary information of Strata Oncology Inc., except as may be required by federal, state or local laws or regulation, and may not be disclosed to others without prior written permission of Strata.

Page 22 of 56

on the personalized ctDNA assay which are averaged together to create a mean VAF. Any participant who has a <50% ratio is defined as a responder.

3.2.3 DISEASE-FREE SURVIVAL

Disease-free survival (DFS) is defined as the time from date of first dose until disease recurrence or death from any cause. The most frequent use of this endpoint is in the adjuvant setting after definitive surgery or radiotherapy and is a recommended clinical endpoint based on FDA's guidance Clinical Trial Endpoints for the Approval of Cancer Drugs and Biologics.¹¹

4 STUDY DESIGN

4.1 OVERALL DESIGN

Participants who are 18 years of age or older, have been diagnosed with histologically documented solid tumors, have an eligible biomarker profile, and are planned for treatment may be eligible for this study according to the criteria in **Sections 5.1-5.2** and the supplemental criteria in the specific biomarker/drug cohort appendix.

Each biomarker/drug cohort will be described in an appendix to this study protocol. Appendix information includes investigational product overview, rationale for biomarker/drug combination, additional cohort-specific eligibility criteria, study treatment including dosing and administration guidelines, along with known adverse reactions.

After obtaining informed consent, study staff shall assess individual participant eligibility using the criteria in **Sections 5.1-5.2** and the supplemental criteria in the specific appendix they are targeting for enrollment. The designated study staff will enter the participant's details into the electronic data capture (EDC) to support a sponsor-required confirmation of biomarker eligibility. Upon confirmation of eligibility and informed consent procedures, the participant will be formally enrolled into the study. Participants will be treated with the applicable cohort's study drug according to dosing instructions in the approved product labeling or provided Investigator's Brochure (IB).

For participants who exhibit more than 1 eligible biomarker result, the treating physician should determine the most appropriate cohort assignment. Factors for consideration include the drug's dosing and administration guidelines, as well as the commercially available product prescribing instructions or provided IB.

A leftover tumor specimen (if historical comprehensive genomic profiling (CGP) and/or ribonucleic acid (RNA) profiling results are not available for submission) and blood sample for ctDNA analysis will be collected at study entry (prior to therapy start). Blood samples will be

The information contained in this protocol and all other information relevant to this study are confidential and proprietary information of Strata Oncology Inc., except as may be required by federal, state or local laws or regulation, and may not be disclosed to others without prior written permission of Strata.

Page 23 of 56

collected and CT/MRI scans will be performed until treatment discontinuation as outlined in the Study Schedule of Activities (SOA) (**Section 7.2**).

Tumor assessments to support ORR efficacy assessment will be completed as outlined in the Study Schedule of Activities (**Section 7.2**) and recorded in the study database. Study staff will also record information in the study EDC (either manually or through an integrated mechanism) which occur as part of standard of care visits. Standard of care details such as demographics, clinical characteristics, and concomitant medications will be recorded within the study database. Upon identification of any efficacy signal, additional real-world data collection may be requested (i.e., additional medical history and imaging) to support additional analysis and cohort expansion studies. Following completion of or discontinuation from drug, all active study participants will be followed for survival for 3 years from the date of consent.

This study will require reporting of Common Terminology Criteria for Adverse Events (CTCAE) grade 3 and 4 AEs that are possibly, probably, or definitely related to the study treatment. All SAEs, regardless of grade, relatedness to study drug, or expectedness, must be reported, including deaths.

Drug/biomarker cohorts may be added, changed, or discontinued over time. This study may enroll up to 700 participants.

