This study may also include separate cohorts of patients in the micro-metastatic setting (as defined by ctDNA positive liquid biopsy) post-standard of care adjuvant therapy, but not yet having been identified as traditionally advanced or metastatic using standard of care imaging or biochemical testing. All therapies are FDA-approved in oncology with demonstrated safety profiles in the traditionally advanced setting; the toxicity profile may be different in the micro-metastatic setting. The utility of targeted therapy in the early-stage setting has been demonstrated with the approval of osimertinib for patients with EGFR-mutated NSCLC. The ADAURA trial demonstrated that osimertinib was well tolerated post-resection in patients with stage IB-III NSCLC; dose reductions due to adverse events occurred in 9% of patients in the treatment group.⁶ This was comparable to the 10% dose reduction rate observed in first-line patients with advanced NSCLC at the same recommended dose.⁷ Comparatively, the toxicity profile of immunotherapies in early-stage disease may not be as favorable. Dose discontinuation due to adverse events occurred in only 9% of patients with advanced melanoma treated with pembrolizumab in KEYNOTE-001, while 14% of melanoma patients that received pembrolizumab as adjuvant therapy post resection in KEYNOTE-054 experienced adverse event related dose discontinuation.^{8,9} Recently announced data from KEYNOTE-564, however, suggests that the toxicity profile of pembrolizumab when used as adjuvant therapy in patients with renal cell carcinoma following nephrectomy was consistent with previously reported studies with the anti-PD-1 therapy.¹⁰ To monitor risk and capture any differences in toxicity profiles between patient populations, full safety data collection will be collected in this study.

More information on the clinical data associated with each therapeutic study arm and known and expected benefits, risks, and reasonably expected adverse events (Aes) may be found in the corresponding appendices.

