6.4 STUDY AGENT DISCONTINUATION

Discontinuation of dosing does not mean discontinuation from the study. Remaining study procedures should be completed as indicated by the study protocol regardless of whether the participant is on active treatment. If a clinically significant finding is identified (including, but not limited to, changes from baseline) after enrollment, the investigator or qualified designee will determine if any change in study drug administration is needed. Any new, clinically relevant finding that is both unexpected and thought to be related to the drug will be reported as an SAE under Other Medically Important Event as described in Section 8.2.2. All AEs and SAEs will be reported and captured in the CRF.

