8.2.4 TIME PERIOD AND FREQUENCY FOR EVENT ASSESSMENT AND FOLLOW-UP

The occurrence of an AE or SAE may come to the attention of study personnel during study visits and interviews of a study participant presenting for medical care, or upon review by a study monitor.

All AEs, including local and systemic reactions not meeting the criteria for SAEs, will be captured on the appropriate CRF. Information to be collected includes event description, time of onset, investigator's assessment of severity, relationship to study product (assessed only by those with the training and authority to make a diagnosis), and time of resolution/stabilization of the event. Regardless of relationship, all AEs occurring while on study must be documented and followed to adequate resolution.

Any medical condition that is present at the time that the participant is screened will be considered as baseline and not reported as an AE. However, if the study participant's condition deteriorates at any time during the study, it will be recorded as an AE.

Changes in the severity of an AE will be documented to allow an assessment of the duration of the event at each level of severity to be performed. AEs characterized as intermittent require documentation of onset and duration of each episode.

The information contained in this protocol and all other information relevant to this study are confidential and proprietary information of Strata Oncology Inc., except as may be required by federal, state or local laws or regulation, and may not be disclosed to others without prior written permission of Strata.

Page 42 of 56

Study site will record all reportable events with start dates occurring any time after informed consent is obtained until 7 (for non-serious AEs) or 30 days (for SAEs) after the last day of study participation. At each study visit, the investigator will inquire about the occurrence of AE/SAEs since the last visit. Events will be followed for outcome information until resolution or stabilization.

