8.2.6 SERIOUS ADVERSE EVENT REPORTING

The investigator will immediately report any SAE to the sponsor, whether or not it is considered study intervention related, including those listed in the protocol or package insert. The report must include an assessment of whether there is a reasonable possibility that the study intervention caused the event. Study endpoints that are SAEs (e.g., all-cause mortality) must be reported in accordance with the protocol unless there is evidence suggesting a causal relationship between the study intervention and the event (e.g., death from anaphylaxis). In that case, the investigator must immediately report the event to the sponsor.

All SAEs will be followed until satisfactory resolution or until the investigator deems the event to be chronic or the participant is stable. Other supporting documentation of the event may be requested by the study sponsor and should be provided as soon as possible.

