8.2.8 EVENTS OF SPECIAL INTEREST

All deaths that occur during the study must be reported as follows:

- Death that is clearly the result of disease progression should be documented but not reported as an SAE.
- Where death is not due (or not clearly due) to progression of the disease under study, the AE causing the death must be reported as an SAE within 24 hours of knowledge of the event.
- Deaths with an unknown cause should always be reported as an SAE.

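### The protocol gives conflicting safety-reporting rules: Section 4.1 against 8.2.8 on progression deaths, Section 4.1 against 6.4 on AE scope, and the post-treatment text against Tables C and D

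*Protocol*

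**What the plan says.** **Deaths.** Section 4.1 reads "All SAEs, regardless of grade, relatedness to study drug, or expectedness, must be reported, including deaths". Section 8.2.2 names death among the outcomes that make an event serious. Section 8.2.8, which deals only with deaths, reads "Death that is clearly the result of disease progression should be documented but not reported as an SAE". Section 8.2.6 opens with "The investigator will immediately report any SAE to the sponsor, whether or not it is considered study intervention related", then adds "Study endpoints that are SAEs (e.g., all-cause mortality) must be reported in accordance with the protocol", with immediate reporting of such endpoint events kept for those with evidence of a causal link to treatment.

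**AE scope.** Section 4.1 requires reporting of "grade 3 and 4 AEs that are possibly, probably, or definitely related to the study treatment". Section 6.4 says "All AEs and SAEs will be reported and captured in the CRF". Section 8.2.4 puts all AEs on the CRF and adds "Regardless of relationship, all AEs occurring while on study must be documented and followed to adequate resolution". Section 2.3 promises that "full safety data collection will be collected in this study", so that differences in toxicity between patient populations can be seen.

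**After treatment.** Table C (tdMeta) marks AEs and SAEs at the Post-Treatment visit, and Table D (μMeta) marks its Safety Evaluation row there. Sections 7.2.2.4 and 7.2.3.4 list medical history, concomitant medications and standard-of-care procedures for that period. They list no AE or SAE item and rule out further study-specific procedures. Section 8.2.4 collects events until 7 days (non-serious AEs) or 30 days (SAEs) after participation ends.

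**The concern.** SAE incidence is the only safety endpoint in Table A (tdMeta) and in Table B (μMeta). If sites or the sponsor apply different rules to progression deaths, the same death counts as an SAE under one section and not under the other. The tdMeta cohorts enrol people with advanced disease and few or no options (Section 2.3) and follow survival for 3 years from consent, so progression deaths are to be expected.

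The AE scope decides which records exist for the safety analysis in Section 9.3.3. It also decides whether the aim in Section 2.3 can be met, since that section warns that toxicity may differ in the micro-metastatic setting. A classification of deaths can be corrected at analysis if the deaths are on file. An AE that was never entered cannot be restored. These are collection rules, so they have to be right in the protocol; an analysis plan cannot mend them.

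**Working it through.** No arithmetic applies. The check sets the rules side by side.

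**1. Progression deaths**
- 4.1: all SAEs are reported, deaths included, whatever the relatedness or expectedness. No exception and no reference to Section 8.2.
- 8.2.8: a death clearly due to progression is documented and is not reported as an SAE. Deaths not clearly due to progression, and deaths of unknown cause, are SAEs.
- 8.2.6: endpoint events such as all-cause mortality are taken out of the immediate-report rule and referred to the protocol.

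A death clearly due to progression is a reportable SAE under 4.1 and is not one under 8.2.8. The two rules cannot both govern that death. Section 8.2.6 does not settle the matter, because it points back to a protocol that holds both rules.

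**2. AE scope**
- 4.1: grade 3 and 4, at least possibly related. Its next sentence covers SAEs of any grade and any relatedness.
- 6.4: all AEs, both reported and entered in the CRF.
- 8.2.4: all AEs captured on the CRF, whatever the relationship. The same section later tells sites to record reportable events without saying which events those are.
- 2.3: full safety data, with no grade or causality limit.

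The difference between 4.1 and 6.4 is therefore the set of non-serious AEs that are below grade 3, or that are judged unlikely or not related. The conflict with 6.4 is direct, because both sections speak of reporting. Sections 8.2.4 and 2.3 speak of capture and collection. They could be squared with 4.1 if the protocol separated CRF capture from reporting to the sponsor, but it states no such separation.

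Section 9.3.3 analyses the incidence of ADRs and ADEs. If a site follows 4.1, lower-grade non-serious events are absent from that analysis. So are unrelated events, to the extent that the analysis is meant to include them.

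**3. After discontinuation**
- Tables C and D: safety marked at Post-Treatment.
- 6.4: remaining study procedures continue whether or not the participant is on treatment.
- 8.2.4: collection runs past the end of participation.
- 7.2.2.4 and 7.2.3.4: no AE or SAE item, and no further study-specific procedures.
- 7.1.1: AE and SAE evaluation is classed as a study-specific procedure.

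The Baseline and On Treatment lists (7.2.2.2, 7.2.2.3, 7.2.3.2, 7.2.3.3) each carry an AE/SAE line. The post-treatment lists do not, and read together with 7.1.1 their text would exclude it. Three places say that collection continues, and the two parallel post-treatment sections point the other way.

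**The case against.** The strongest reply is that a specific rule overrides a general one. Section 8.2.8 concerns only deaths, and it opens by saying how all of them are to be reported, so 4.1 can be taken as a summary. That is a sensible reading, but nothing in 4.1 tells a site to adopt it.

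A reader might infer more than the text supports in five places.

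- *That 8.2.6 also contradicts 8.2.8.* It does not. Its general sentence requires every SAE to be reported at once, but the sentence on endpoint events exempts all-cause mortality unless causality is suspected and defers to the protocol. That is compatible with 8.2.8.
- *That 4.1 restricts AE reporting to related grade 3 and 4 events.* It says such events must be reported and does not say only these. It can be read as a minimum, so 2.3 and 8.2.4 sit badly with it but conflict with it less directly than 6.4 does.
- *That safety collection stops at discontinuation.* The weight of the text favours continued collection. The post-treatment sections contain an omission at odds with the schedule.
- *That the end of the collection window is open.* Section 4.3, the follow-up footnotes to Tables C and D, and 7.2.2.4 largely settle it as 3 years from consent or death. Section 8.2.4 only fails to refer to them.
- *That deaths are lost.* Progression deaths remain documented under 8.2.8, and overall survival counts death from any cause.

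It can also be said that the operations manual and cohort appendices, which are not shown, may already guide sites. That may limit the practical harm, but the protocol must still agree with itself.

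**Conclusion.** The protocol is wrong as written on three linked points. The rule on progression deaths in 4.1 contradicts 8.2.8. The AE scope in 4.1 conflicts directly with 6.4 and sits badly with 8.2.4 and 2.3. The post-treatment sections leave out the safety collection that the schedule, 6.4 and 8.2.4 require.

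No numerical size can be given, because the protocol states no SAE, AE or death rates. What is affected is the numerator of SAE incidence in every cohort and the content of the AE analysis. The primary endpoints and overall survival do not depend on these rules. The death conflict can be repaired at analysis as long as the deaths are documented as 8.2.8 requires. The AE conflict cannot, and this is the main reason to settle it in the protocol. The practical consequence assumes that at least some sites take 4.1 or the post-treatment lists at face value. The documents do not show whether any have.

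**What to change.** - Reconcile 4.1 with 8.2.8 into one rule on whether progression deaths count as SAEs. This review does not say which.
- Reconcile 4.1 with 6.4 and 8.2.4 into one AE-scope rule consistent with 2.3. Have 4.1 cross-refer to Section 8.2, and tie the reportable events in 8.2.4 to that rule. If a split between CRF capture and reporting to the sponsor is intended, state it.
- Make 7.2.2.4 and 7.2.3.4 agree with Tables C and D and with 8.2.4 on AE and SAE collection after discontinuation.
- Tie the end of participation in 8.2.4 to the definition in 4.3 (3 years from consent, or death).
- Because sites may already have followed either death rule, derive SAE incidence in the same way for all participants from the documented deaths. A table with and without progression deaths is an optional way to show this.

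The cost is text edits in 4.1, 6.4, 7.2.2.4, 7.2.3.4 and 8.2, and possible back-entry of events at sites that followed the narrower AE rule.
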